**Anticipated AEs may be reported with the Continuing Review/Progress Report.**

*Describe your plan for reporting to the JHSPH IRB, local IRBs, and (if applicable) to the sponsor. Include your plan for government-mandated reporting of child abuse or illegal activity.*

Given the nature of the study, we do not anticipate any adverse events or serious adverse events. However, the PI will evaluate the event and promptly submit written reports of all events that meet the definition of “unanticipated problems involving risks to participants and other,” in accordance with the Johns Hopkins Bloomberg School of Public Health (JHSPH) IRB Policy No. 103.06 – “Reports of unanticipated problems involving risks to participants or to others (Problem/event reporting)” to the JHSPH IRB and the MUHAS IRB, using designated reporting forms, as soon as possible after she learns of the event, but in all cases within 10 working days. If the unanticipated adverse event is deemed alarming by the Project PI, she will immediately report the event to the respective IRB offices.

E. **Other IRBs/Ethics Review Boards:**

*If other IRBs will review the research, provide the name of each IRB/ethics review board and its Federal Wide Assurance number, if it has one (available on OHRP’s website at <http://www.hhs.gov/ohrp/assurances>). For federally funded studies, subrecipients MUST have a Federal Wide Assurance (FWA) number from the OHRP. The IRB overseeing the subrecipient should be registered with the OHRP. The JHSPH IRB will not have oversight responsibility for international subrecipients, and generally will not oversee data collection at external U.S. institutions. Please contact [[contact]](mailto:[contact]) with questions.*

Non-JHSPH IRB/REC	FWA Number
Research Ethics Committee	FWA00004301
Directorate of Research and Publications, Muhibili University of Health and Allied Sciences (MUHAS)	

--	--

**F. “Engaged” in Human Subjects Research:**

*For studies that involve collaboration with non-JHSPH institutions, complete the chart below by describing the collaboration and the roles and responsibilities of each partner, including the JHSPH investigator. This information helps us determine what IRB oversight is required for each party. Complete the chart for all multi-collaborator studies.*

**Insert collaborator names and FWA numbers, if available. Note who will be “engaged” in human subjects research by filling in the following table:**

	JHSPH	MUHAS	
For federally funded studies, collaborators' FWA	00000287	00004301	
Primary Grant/Contract Recipient	X		
Grant/Contract Subrecipient		X	
Hiring Data Collectors		X	
Training Data Collectors	X	X	
Obtaining Informed Consent and/or Identifiable Data		X	
Accessing/Analyzing Identifiable Data	X	X	
Overseeing storage, access and use of biospecimens	N/A	N/A	

**COMPLETE THE FOLLOWING SECTIONS WHEN RELEVANT TO YOUR STUDY:**

**XI. Secondary Data Analysis of Existing Data:**

**A. Study Design:**

1. *Describe your study design and methods. The study design must relate to your stated aims/objectives.*

We will use a limited, longitudinal study design to detect changes in preliminary outcomes of MAT clients participating in the Stage 2 pilot trial. We will extract data from the MAT clinic records of the 20 participating MAT clients:

- Time enrolled in MAT
- Time since HIV diagnosis (if relevant)
- Methadone dose
- Drug use (heroin, cocaine, cannabis or benzodiazepines)

- Alcohol use
- Methadone adherence
- Antiretroviral therapy (ART) adherence (pharmacy refills)

We will assess changes in substance use (via drug test results), alcohol use (via breathalyzer tests), methadone adherence, and HIV treatment adherence (for clients living with HIV). Data will be extracted for the six-month period prior to the intervention and the six-month period following the end of the intervention.

2. *Provide an estimated sample size and an explanation for that number.*

We will include 20 current MAT clients at the Muhimbili MAT Clinic in our sample. This includes all MAT clients who will participate in the pilot trial.

3. *Provide a brief data analysis plan and a description of variables to be derived.*

We will use descriptive statistics to characterize MAT clients participating in the pilot trial. We compare trends in methadone and ART adherence for the 6-month period prior to the intervention and 6-month period after the intervention.

**B. Participants:**

1. *Describe the subjects who provided the original data and the population from which they were drawn.*

Participants will be current MAT clients at the Muhimbili MAT Clinic who participate in the pilot trial.

*Note: If you are receiving, accessing, or using data from a U.S. health care provider, the need for HIPAA review is likely. If you plan to bring identifiable health information from a foreign country to a U.S. covered entity (e.g., lab at the Hopkins SOM), HIPAA may be triggered. If either of these conditions is met, check “yes” to the HIPAA question in the PHIRST application.*

2. *If you plan to analyze human specimens or genetic/genomic data, provide details about the source of those specimens and whether they were collected using an informed consent document. If yes, explain whether your proposed use is “consistent with” the scope of the original consent, if it potentially introduces new analyses beyond the scope of the original consent, and/or if it introduces new sensitive topics (HIV/STDs, mental health, addiction) or cultural/community issues that may be controversial.*

N/A

3. *Explain whether (and how) you plan to return results to the participants either individually or as a group.*

We will not return the results of these analyses to participants as the data collected will come from clinical records and all participants will be clients who receive standard of care and undergo standard procedures for detection of drug and alcohol use or low adherence to methadone or ART.

**XII. Oversight Plan for Student-Initiated Studies:**

A. *For student-initiated studies, explain how the PI will monitor the student’s adherence to the IRB-approved research plan, such as communication frequency and form, training, reporting requirements,*

*and anticipated time frame for the research. Describe who will have direct oversight of the student for international studies if the PI will not personally be located at the study site, and their qualifications.*

- B. *What is the data custody plan for student-initiated research? (Note: Students may not take identifiable information with them when they leave the institution.)*

**XIII. Creation of a Biospecimen Repository:**

*Explain the source of the biospecimens, if not described above, and what kinds of specimens will be retained over time. Clarify whether the specimens will be obtained specifically for repository purposes, or will be obtained as part of the core study and then retained in a repository.*

- A. *Describe where the biospecimens will be stored and who will be responsible for them.*
- B. *Describe how long the biospecimens will be stored, and what will happen at the end of that period.*
- C. *Explain whether the biospecimens will be shared with other investigators, inside and outside of JHU, how the decision to share will be made, and by whom. Include your plans, if any, for commercial use. Also explain how downstream use of the specimen will be managed, and what will happen to left-over specimens.*
- D. *Describe whether future research using the biospecimens will include specimen derivation and processing (cell lines, DNA/RNA, etc.), genomic analyses, or any other work which could increase risk to participants. Explain what additional protections will be provided to participants.*
- E. *If future research could yield unanticipated incidental findings (e.g., an unexpected finding with potential health importance that is not one of the aims of the study) for a participant, do you intend to disclose those findings to the study participant? Please explain your position.*
- F. *Explain whether the specimens will be identifiable, and if so, how they will be coded, who will have access to the code, and whether the biospecimens will be shared in linked (identifiable) form.*
- G. *Explain whether the repository will have Certificate of Confidentiality protections.*
- H. *Explain whether a participant will be able to withdraw consent to use a biospecimen, and how the repository will handle a consent withdrawal request.*

- I. *Describe data and/or specimen use agreements that will be required of users. Provide a copy of any usage agreement that you plan to execute with investigators who obtain biospecimens from you.*

#### **XIV. Data Coordinating Center:**

*Complete if JHSPH serves as the Data Coordinating Center.*

- A. *How will the study procedures be developed?*
- B. *How will the study documents that require IRB approval at each local site be developed? Will there be some sort of steering or equivalent committee that will provide central review and approval of study documents, or will template consent forms, recruitment materials, data collection forms, etc. be developed by and provided to the local sites by the coordinating center without external review?*
- C. *Will each local clinical site be overseen by its own IRB with an FWA, or will a Single IRB review the study? State whether the coordinating center will collect IRB approvals and renewals from the clinical centers; if not, explain why.*
- D. *How will the coordinating center provide each local site with the most recent version of the protocol and other study documents? What will be the process for requesting that these updates be approved by local clinical center IRBs?*
- E. *What is the plan for collecting data, managing the data, and protecting the data at the coordinating center?*
- F. *What is the process for reporting and evaluating protocol events and deviations from the local sites? Who has overall responsibility for overseeing subject safety: the investigators at the recruitment site, the Coordinating Center, the Steering Committee, or a Data and Safety Monitoring Board (DSMB)? Is there a DSMB that will evaluate these reports and provide summaries of safety information to all the reviewing IRBs, including the coordinating center IRB? Please note that if there is a DSMB for the overall study, then the coordinating center PI does not have to report to the coordinating center IRB each individual adverse event/problem event that is submitted by the local site PIs.*
- G. *Some FDA regulated studies have different AE reporting criteria than that required by the IRB (IRB Policy No. 103.06). How will you reconcile the different requirements, and who is responsible for this reconciliation?*

H. Who is responsible for compliance with the study protocol and procedures and how will the compliance of the local sites be monitored and reviewed? How will issues with compliance be remedied?

**XV. Drug Products, Vitamins, Food and Dietary Supplements:**

Complete this section if your study involves a drug, botanical, food, dietary supplement or other product that will be applied, inhaled, ingested or otherwise absorbed by the study participants. If you will be administering drugs, please upload the product information.

A. List the name(s) of the study product(s), and the manufacturer/source of each product.

Name of Study Product	Manufacturer/Source

B. List each study product by name and indicate its approved/not approved status.

Approved by the FDA and Commercially Available	Approved by Another Gov't Entity (provide name)	Cleared for Use at Local Study Site

C. If your study product has an Investigational New Drug (IND) application through the U.S. Food and Drug Administration, provide the IND number, and the Investigators Brochure.

a. Who will hold the IND?

D. If your study product is a marketed drug, provide the package inserts or other product information. If the study product WILL NOT be used for its approved indication, dose, population, and route of administration, provide a detailed rationale justifying the off-label use of the study product.

E. If the study product does not require FDA approval (e.g., dietary supplements, botanicals, products not subject to the U.S. FDA, etc.), provide safety information (as applicable) and a certificate of analysis.

- F. Explain who will be responsible for drug management and supply, labeling, dispensing, documentation and recordkeeping. Complete and upload into PHIRST the Drug Data Sheet available on the JHSPH IRB website at [www.jhsph.edu/irb](http://www.jhsph.edu/irb).
- G. What drug monitoring and/or regulatory oversight will be provided as part of the study? Please describe.

#### **XVI. Medical Devices:**

Complete this section if your study will involve an approved or investigational medical device (**diagnostic**, non-significant risk, significant risk).

- A. List the name(s) of the study product(s), the manufacturer/source of each product, and whether or not it is powered (electric, battery). Provide product information. If it is electric, upload documentation of clinical engineering approval or its equivalent from a local authority, to ensure that the device is in good working order.

Name of Study Product	Manufacturer/Source	Powered?

- B. List each study product by name and indicate its status as approved by a government authority or not approved.

Approved by the FDA and Commercially Available	Approved by Another Gov't Entity (provide name and approval information)	Not Approved

- C. If your investigational device is Exempt from the FDA IDE regulations, explain which section of the code applies to your device and why it meets the criteria provided. If it is a **diagnostic device**, provide pre-clinical information about the sensitivity and specificity of the test and the anticipated failure rate. If you plan to provide the results to participants or their physicians, justify doing so, and explain how those results will validated (or not) against the current “gold standard”.
- D. If you believe the investigational device is not IDE exempt under 21CFR 812.2(c), but is a “Non-Significant Risk” device considered to have an approved IDE application, provide information from the manufacturer supporting that position.
- E. If you are using an investigational device that is a Significant Risk Device, provide the IDE number given by the FDA, or if not under FDA jurisdiction, explain why it is appropriate to use this device in this study. Provide a description of the device, and upload a picture or manufacturing schematics into PHIRST. Provide any other information relevant to a determination of its safety to be used for the purposes outlined in this research plan.

Study Title: Social Networks and Methadone Maintenance Treatment Retention and Antiretroviral Therapy Retention in Tanzania

Document: Statistical Analysis Plan (ID: IRB00019420)

NCT number: NCT04479475

Document date: 8/11/2025

PI Name: [name]

Study Title: Adaptation and Pilot of a Social Network Intervention to Improve Retention in Medication-Assisted Treatment for Opioid Use Disorder in Tanzania

Data Analysis Plan

I. Descriptive Analyses

- a. Baseline characteristics
 - i. Summarize participant demographics (age, gender, education, housing status, employment status, etc.)
 - ii. Describe baseline clinical characteristics (confirmed HIV status, methadone dosage, missed methadone doses in the past 30 days, ART refills in the past 6 months (for participants with confirmed HIV-positive status)
 - iii. Statistics: Means (SD) and medians (IQR) for continuous variables, counts and percentages for categorical variables

II. Primary outcomes: Acceptability and Feasibility

- i. Intervention completion rates and individual session attendance for enrolled MMT clients and social support persons. Number of participants lost to follow-up or number who voluntarily withdrew from the study.
- ii. Content or thematic analysis of implementation facilitators and barriers/challenges, including any protocol deviations, as reported in follow-up, qualitative interviews with participants and intervention counselors, as well as in supervision meetings throughout the intervention implementation period.
- iii. Reported fidelity from intervention counselors, as reported in supervision meetings throughout the intervention implementation period, as well as in follow-up, qualitative interviews with counselors.

III. Secondary outcomes: Missed Methadone Doses and ART refills

- a. Secondary outcomes will be assessed for MMT client participants only.
- b. *Change in missed methadone doses in the past 30 days:* Use the Wilcoxon signed-rank test to compare the number of missed methadone doses at baseline and follow-up. Report the median differences, mean differences for changes in missed doses, and the exact p-value.
- c. *Change in pharmacy ART refills in the past 6 months* (HIV-positive participants only): Conduct cross-tabulation to compare ART refill status at baseline and follow-up. Use McNemar's test to examine changes in refill status across the two time points. Report the proportions of participants refilling ART, the odds ratio, and the exact p-value.

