## JHSPH IRB Research Plan for New Data Collection

21Sep2021

*For new data collection, new data collection plus secondary data analysis, biospecimen repositories, and data coordinating center protocols.*

**PI Name:** [name]

**Study Title:** Adaptation and Pilot of a Social Network Intervention to Improve Retention in Medication-Assisted Treatment for Opioid Use Disorder in Tanzania

**IRB No.:** IRB00019420

**PI Version No. / Date:** Version 3.0/04.4.2023

**I. Aims of the Study:** *Describe the aims/objectives of the research and/or the project's research questions or hypotheses.*

The primary aim of this study is to adapt, pilot, and assess the acceptability and feasibility of a social network intervention intended to improve retention in medication-assisted treatment for opioid use disorder. A secondary aim is to assess the potential effect of the intervention on antiretroviral adherence among individuals enrolled in medications for opioid use disorder who are also living with HIV.

**II. Background and Rationale:** *Explain why this study is being done. Summarize briefly what is already known about the issue and reference previously published research, if relevant.*

People who inject (PWID) drugs in Tanzania have high rates of HIV. The elevated HIV risks associated with injection drug use have been well documented (41). Globally, PWID have 28 times higher HIV prevalence than the general adult population (42). In Tanzania, estimates of HIV prevalence among PWID, have ranged from 35% to 50% (9-11) compared to 5.1% in the general population (12). HIV rates are even higher among women, with prevalence estimates among women who use drugs reaching upwards of 66% (10, 13).

Medication-assisted treatment (MAT) for opioid use disorder is recommended as part of a comprehensive package of interventions for the prevention, treatment, and care of HIV infection among PWID (14). People retained in MAT have lower HIV risk (15, 16), reduced rates of overdose and mortality (17), greater access to other services (18), and greater likelihood of positive treatment outcomes (43-46). Among HIV-positive (HIV+) PWID, retention in MAT is associated with antiretroviral (ART) adherence and HIV viral suppression (8).

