**A. Inclusion Criteria:**

**Stage 1:** Inclusion criteria for key informant interviews will be: 1) at least 18 years old, 2) current provider or staff person at the Muhimbili MAT clinic OR current community outreach workers/staff person at a Dar es Salaam-operating CBO providing outreach to people who use drugs.

Inclusion criteria for focus group discussions will be: 1) at least 18 years old, 2) a current Muhimbili MAT client OR a person identified by a current Muhimbili MAT clients as a social support person OR

current community outreach workers/staff person at a Dar es Salaam-operating CBO providing outreach to people who use drugs.

Inclusion criteria for the key stakeholder meeting will be: 1) at least 18 years old, 2) a government representative involved in decision-making on opioid use disorder treatment programs in Tanzania OR a key stakeholder from civil society organizations focused on outreach and other programming for people who use drugs OR a MAT clinic provider OR a topical expert relevant to the adapted intervention (e.g., social support interventions or economic strengthening interventions).

**Stage 2:** Inclusion criteria for MAT client participants in the intervention pilot will be: 1) 18 years old or older, 2) currently enrolled in the MAT program at the Muhimbili MAT clinic, 3) prescribed methadone for the past 3 months, 4) received a positive test result for heroin, cannabis or alcohol use in the past 3 months, 5) provide consent for trial participation.

Inclusion criteria for social support persons in the intervention pilot will be: 1) 18 years old or older, 2) identified as a social support person of a MAT client participating in the pilot trial, 3) lives in Dar es Salaam, 4) provide consent for trial participation.

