For Phase 5, we will identify and recruit topical experts based on recommendations from the local study team. The local co-PI will reach out directly to potential topical experts and other key stakeholders to invite them to a key stakeholder workshop.

**Stage 2:** We will pilot the intervention with a maximum of 80 people: 20 current MAT clients at the Muhimbili MAT Clinic and up to 60 social support persons identified by recruited MAT clients. Muhimbili MAT clinic staff will compile a list of clients who have tested positive for heroin, cannabis, and alcohol based on monthly urine screen in the past 3 months or random alcohol breathalyzer test in the past 3 months. The list will be stratified by HIV status to obtain equal number of MAT clients with and without HIV. From the list, the research team will randomly select 10 clients with HIV and 10 clients without HIV. MNH MAT clinic staff will introduce the study to the selected MAT clients who meet study eligibility and refer those interested in participating to the study team.

During the social mapping session of the intervention, MAT client participants will be asked to identify up to three people who provide them with support to invite them to participate in the intervention. MAT clients will be provided a letter to give to each of the social support persons identified and will provide the study team with the phone numbers of the social support persons, if available. The recruitment letter will include the contact information for the local co-PI. If a phone number for a social support person is provided, the study team will attempt to contact the identified social support person up to three times. The study team will only contact social support persons identified by participating MAT clients after the MAT client has informed the social support person of the study and the social support person is expecting to hear from study staff. The study team will confirm with the MAT client that social support persons have been informed of the study through the recruitment letter and/or vocally. Once contact with the identified social support person is made, a member of the study team will introduce the study to the social support person and invite them to participate in the study.

2. *Address any privacy issues associated with recruitment. If recruitment itself may put potential participants at risk (if study topic is sensitive, or study population may be stigmatized), explain how you will minimize these risks.*

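### The ART-refill comparison in SAP III.c takes in every HIV-positive participant, so a first start of ART can be counted as a gain in adherence

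*SAP*

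**What the plan says.** Protocol section I gives the purpose: "A secondary aim is to assess the potential effect of the intervention on antiretroviral adherence among individuals enrolled in medications for opioid use disorder", specifically those who also live with HIV. Section XI.A.1 makes pharmacy refills the measure of ART adherence. It takes data from clinic records for the six months before the intervention and the six months after it ends.

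Nothing in the selection of clients refers to ART. The Stage 2 criteria in section IV.A cover age, MAT enrolment, methadone prescription, a recent positive test and consent, and section IV.B has no Stage 2 exclusions. For the draw, section V.A.1 says "the research team will randomly select 10 clients with HIV and 10 clients without HIV".

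SAP III.c restricts the refill analysis by HIV status alone. The instruction is to "Conduct cross-tabulation to compare ART refill status at baseline and follow-up" and then: "Use McNemar's test to examine changes in refill status across the two time points". The outputs are the proportions refilling, an odds ratio and an exact p-value. The baseline description in SAP I.a.ii uses the same HIV-positive group.

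The record extraction in section XI.A.1 includes time since HIV diagnosis, but no ART start date and no on-ART indicator. Refill status is not defined in either document.

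**The concern.** Adherence can be measured only in someone who has been prescribed the drug. A client with HIV who has never started ART has nothing to refill. If the denominator is all HIV-positive participants, the obvious entry for that client at baseline is no refill.

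Two things can follow:

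- The client starts ART during the intervention or the follow-up window. The pair moves from no to yes, which McNemar's test and the odds ratio read as improvement.
- The client never starts. The pair is no at both times, which lowers both reported proportions and looks like persistent non-adherence.

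A first start can produce only a favourable switch, never an unfavourable one, and there is no comparison arm to show how many starts would be expected anyway.

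The planned data cannot sort this out afterwards. Time since diagnosis identifies recent diagnoses, but not clients diagnosed long ago and never treated. With refills taken only from the two windows, a first start looks the same as a return to ART after a lapse. The second is a real change in adherence; the first is not.

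**Working it through.** The documents give no power, alpha or effect size for this analysis, so there is no figure of the plan's own to reproduce. The one related count is consistent: 10 clients with HIV + 10 without = 20 MAT clients.

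**Inputs**

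- HIV-positive clients: n = 10 (protocol V.A.1).
- Test: exact McNemar (SAP III.c). Sidedness is not stated; two-sided is assumed.
- ART coverage among HIV-positive clients: not in the documents, so varied below.

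**Formula.** Let b be the number of no-to-yes pairs and c the number of yes-to-no pairs. Then p = min(1, 2 × P(X ≥ max(b, c))), with X binomial(b + c, 0.5). When c = 0 this is min(1, 2 × 0.5^b). The matched odds ratio is b/c.

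**Starters alone.** Suppose k of the 10 clients have no ART in the whole baseline window and then start, and every other client refills in both windows. Adherence has not changed in anyone. One client is 1/10 = 10 percentage points.

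| k | Refilling at baseline | Refilling at follow-up | Apparent change | Exact p | Clients on ART at baseline: n, change |
|---|---|---|---|---|---|
| 1 | 9/10 = 90% | 100% | +10 points | 2 × 0.5 = 1.0 | 9, 0 points |
| 2 | 8/10 = 80% | 100% | +20 points | 2 × 0.25 = 0.50 | 8, 0 points |
| 3 | 7/10 = 70% | 100% | +30 points | 2 × 0.125 = 0.25 | 7, 0 points |

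In each row c = 0, so the odds ratio b/c is infinite. Restricted to clients on ART at baseline, there are no discordant pairs and no change. Starters alone reach p < 0.05 only at k = 6 (2 × 0.5^6 = 0.031); k = 5 gives 0.0625.

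**Starters added to genuine changes.** With two genuine improvers and one client who worsens, the odds ratio is 2/1 = 2.0 (p = 1.0). One starter makes it 3/1 = 3.0 (p = 0.625). With five genuine improvers and none worse, one starter moves p from 0.0625 to 0.031.

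**How likely it is that someone is off ART.** For assumed coverage q, and treating clients as independent, the expected number off ART is 10 × (1 − q) and the chance of at least one is 1 − q^10.

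| Assumed q | Expected off ART | Chance of at least one |
|---|---|---|
| 95% | 0.5 | 40% |
| 90% | 1 | 65% |
| 80% | 2 | 89% |
| 70% | 3 | 97% |

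These are chances of being off ART, not of starting it. The apparent gain reaches 10 points per client only if that client goes on to start and refill, so the first table is an upper bound for a given number off ART.

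**The case against.** The strongest objection is that the bias depends on a coding rule the documents do not contain. If a client without a prescription were coded as not applicable, the pair would drop out and starters would do no harm. That stands as a limit. It does not remove the point, because neither document provides for such coding and the stated analysis set is everyone who is HIV-positive.

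It can also be said that analysing all clients with HIV is legitimate: the aim is set in that population, the SAP's title speaks of ART retention, and protocol VIII.B counts better access to HIV treatment as a benefit. Moving onto ART may well be worth reporting. But it is a different result from adherence, and the plan gives one number for both.

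A reader might infer several stronger claims that the documents do not support:

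- *That upward bias is established.* It is conditional on unstated coding and on an unknown number of starters.
- *That anyone who begins ART around baseline is miscounted.* If any refill in the window counts as yes, a client who started within the baseline window is already a yes. Only clients with no ART in the whole window are affected.
- *That starters could produce a significant result by themselves.* That takes six of 10.
- *That these starts would have happened without the intervention.* No passage shows this. The absence of a control affects every before-after outcome here.
- *That the sampling is at fault.* The protocol's rule, "The list will be stratified by HIV status to obtain equal number of MAT clients with and without HIV", is a sound way to fill the subgroup.

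Finally, this is a secondary outcome in a pilot that disclaims power for significance (protocol III.B), which limits the seriousness.

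**Conclusion.** The point holds as a mismatch between the outcome's label and its analysis set. The plan calls the outcome adherence, selects on HIV status alone, and collects nothing that would separate a first start from better refilling.

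The size is 10 percentage points and one favourable discordant pair per starter. This assumes that all 10 HIV-positive clients are enrolled and that clients without ART are coded as not refilling. The damage falls mainly on the proportions and the odds ratio, which are the SAP's summary of the ART aim; the p-value is affected only at the margin. The number of clients involved could be zero, and the documents give no means of estimating it. The change should be made before the refill analysis is run, but the point does not touch the primary acceptability and feasibility outcomes.

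**What to change.** 1. Add ART start date to the record extraction in protocol XI.A.1.
2. In SAP III.c, limit the refill-adherence comparison to HIV-positive clients already prescribed ART before the intervention starts. Clients who had started earlier and then lapsed stay in, because their return is an adherence change.
3. Define refill status relative to the time on ART within each window, so that a client who began partway through the baseline window is judged on the part that applies. Add a sensitivity analysis in clients on ART for the whole baseline window.
4. Report HIV-positive clients with no ART by the start of the intervention separately, with a count of those who later start.
5. State the denominator for each of these.

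Using the start of the intervention as the cut-off, and not the first day of the baseline window, avoids labelling people who began ART before the intervention as initiations during the study. Stratification by HIV status need not change.

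The cost is one clinic-record field for about 10 clients and a few sentences in the SAP. The drawback is that the adherence denominator may fall below 10, which makes an already imprecise estimate less precise.
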